Crossovers (stop dapagliflozin therapy in the dapagliflozin treatment arm or initiate dapagliflozin in the control arm) will be indicated clinically by treating physicians. Patients and any treating physician will be asked to call the central coordinating center to discuss any crossover before taking the decision. Any decision will always be made by treating physician, but these will be encouraged to do so only if there is a clear clinical indication for it.

Crossovers will be annotated along with the main reason driving the change. Patients with crossover will remain in the trial and follow ups will be done as per protocol. Since the main endpoint of the study is in an intention-to-treat basis, patients will be analyzed according to randomization regardless crossovers. Post-hoc analysis will take into consideration crossovers and patients adhering to original randomization arm during the entire follow-up of the study will be analyzed (see pre-specified groups).

PREMATURE TERMINATION OF STUDY

This study may be suspended or prematurely terminated if there is sufficient reasonable cause. Written notification, documenting the reason for study suspension or termination, will be provided by the IP to the IRB.

Circumstances that may warrant termination or suspension include, but are not limited to:

- Determination of unexpected, significant, or unacceptable risk to participants.
- Demonstration of efficacy that would warrant stopping.
- Insufficient compliance to protocol requirements.
- Data that are not sufficiently complete and/or evaluable.

DAPAGLIFLOZIN THERAPY STRATEGY

TREATMENT DURING TAVI HOSPITALIZATION (i.e. before randomization)

During the inhospital phase, patients will be treated based on the clinical judgment of their responsible physician, strongly suggesting adherence to the recommendations of Clinical Practice Guidelines.

SGLT-2 THERAPY BEFORE RANDOMIZATION

Randomization for DapaTAVI is at the time of discharge or after hospital discharge (in this case always within 14 first days after TAVI), thus treatment during index hospitalization (i.e. before randomization) is completely at the discretion of the treating physician. Patients receiving SGLT-2 inhibitors before randomization will not included in the trial.

DAPAGLIFLOZIN THERAPY AFTER DISCHARGE (i.e. after randomization)

- DAPAGLIFLOZIN DOSING: Dapagliflozin 10 mg once a day.
- **ROUTE OF ADMINISTRATION:** oral.

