- ACQUISITION OF STUDY MEDICATION: This is a pragmatic trial and dapagliflozin therapy is included in the clinical practice armamentarium. Thus, prescription of dapagliflozin agent will be done by physicians according to randomization arm. The study will not provide with any medication to the study.
- DURATION OF THERAPY: The patient will be maintained with / without dapagliflozin throughout the study period (1 year) if no crossover occurs (see specific section).

MANAGEMENT OF PATIENTS AFTER A THE OCCURRENCE OF AN EVENT

When a patient suffers a clinical event (included or not in the list of clinical endpoints), treating physicians are encouraged to contact the coordinating center and local PI. Patients suffering a clinical endpoint (including those included in the primary composite) will remain in the study and should undergo the scheduled follow-ups.

In the case that a patient suffers any clinical endpoint, it is strongly recommended to manage the patients according to Clincal Practice Guidelines. If the physician feels appropriate to initiate or to stop SGLT-2 inhibitor therapy, this will always prevail. Crossover will be annotated and patients followed-up according to original plan.

In all cases, cardiologists from the research team will be available anytime for discussion about the management of patients.

DATA COLLECTION and STUDY PROCEDURES

STUDY EVALUATIONS / TESTS

DapaTAVI is a pragmatic open label randomized clinical trial. There are no medical specific procedures apart from telephone follow ups and registries consultation. No medical exams or tests will be performed for the study matter. All exams and actions are those clinically indicated and the study investigators will collect data from clinical records.

DATA RECORDING

The following variables will be collected and included in the web-based eCRD.

BASELINE VARIABLES TO COLLECT			
Number	Variable		
Demographic and antropometric data			
1	Age		
2	Sex		
3	Weight		
4	Height		
Cardiovascular risk factors			
5	Hypertension		
6	Diabetes mellitus		
Cardiovascular history			
8	Peripheral artery disease		
9	Ischemic heart disease		
10	Prior myocardial infarction		
11	Prior stroke		
12	Atrial fibrillation		
13	Bundle branch block prior to TAVI		
14	Prior pacemaker		
15	Prior aortic bioprothesis		
16	Prior valvuloplasthy		
Comorbidity			
17	Chronic obstructive pulmonary disease		
18	Chronic kidney disease		
Echocardiographic data (prior to TAVI)			
19	Left ventricular ejection fraction		

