Researchers will be offered with the possibility of completing baseline variables by the coordinating center (University Hospital Álvaro Cunqueiro, Vigo, Spain). For this purpose, a copy of the admission report will be requested. To comply with the protection data law, the admission reports should be sent in a secure system.

When accessing via website, there will an option for "upload admission report". The file containing the report (.pdf or .doc) will be selected and uploaded in the system. Since the variables collected in DapaTAVI are those clinically available, it is expected that most of the information will be contained in the admission report.

When accessing via mobile app, there will a possibility of taking a photograph of the admission report with the mobile camera. To avoid retention of photos of the admission report in the mobile phones, the app will not allow selection of previously done photos, only a direct access to the camera via app.

FOLLOW-UP PROCEDURES

• Specific study follow-up. All patients will be monitored by telephone and through their medical records at 3±1 and 12 months, to know their vital status, development of an end-point event or any adverse effect. Whenever a patient presents a clinical event, the medical history will be requested to the local PI. For the DapaTAVI trial, no specific ECG, echocardiogram, or laboratory monitoring are need, only clinical data.

Local researchers will be offered with the possibility of doing telephone calls from the national coordinating center (Hospital Álvaro Cunqueiro, Vigo, Spain). This will be agreed at the beginning of the study or anytime during the march of the trial (i.e. if a center initially is willing to do telephone follow-ups but later thinks this is not possible, the coordinating center will take over this responsibility anytime).

On phone calls, the following fields will be completed after interacting with the patient/family:

- 1. Vital status (alive/death). If death, cause of death (cardiovascular, non-cardiovascular).
- 2. Any HF hospital readmissions or visit to the emergency department (yes/no).

When the patient died or was admitted to a hospital for any cause which may be related to any of the study endpoints, medical reports will be requested to the local investigator.

- 3. Adherence to randomization arm (yes/no). If no, date (month/year) of crossover, and reason for crossover (free text field).
- 4. Functional health status by the NYHA scale.

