- 6. **Flexibility (adherence)** how different is the flexibility in how participants must adhere to the intervention and the flexibility likely in usual care?
 - Patients receive usual encouragement to adhere to the intervention.
 Medical care providers are encouraged to maintain treatment unless a new clear clinical indication is present. No other measures to improve compliance. (Score 4)
- 7. **Follow-up** how different is the intensity of measurement and follow-up of participants in the trial and the likely follow-up in usual care?
 - Participants are followed as usual care except for 3 additional phone contacts during the follow-up period. (Score 4)

- 8. **Primary outcome** to what extent is the trial's primary outcome relevant to participants?
 - The primary outcome is a composite of hard clinically meaningful endpoints: mortality or HF admission. (Score 5)
- 9. **Primary analysis** to what extent are all data included in the analysis of the primary outcome?
 - Primary analysis is performed applying the intention-to-treat principle in the full dataset, no matter whether compliance. (Score 5)

DATA ANALYSIS SET

> Full Analysis Set:

In this document, the term full analysis set is used to describe the analysis set which is as complete as possible and as close as possible to the intention-to-treat ideal of including all randomized subjects. Participants who fail to satisfy an entry criterion (eligibility violations) will be excluded from this dataset. In order not to introduce bias, the following circumstances have to apply:

- The entry criterion will be measured prior to randomization.
- The detection of the relevant eligibility violations will be made completely objectively.
- o All detected violations of the particular entry criterion will be excluded.

> Per Protocol Set:

The per protocol set is the subset of the subjects in the full analysis set without treatment crossovers. In this data set, participants who switch from their randomized treatment will be therefore censored at the time of their switch.

RANDOMIZATION

Randomization will be performed centrally via a web or dedicated mobile application. Randomization will follow a permuted-block design with varying block sizes to ensure the continued equivalence of each group size and will be estratified according to center.

STATISTICAL PLAN: SAMPLE SIZE CALCULATION, ADAPTIVE DESIGN, INTERIM ANALYSES

SAMPLE SIZE

The number of subjects was determined for the primary endpoint of the trial.

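### The per-protocol set is defined both as patients who never switch and as switchers censored at the switch; the first rule deletes valid first events, with a bias of unknown size and sign

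*Combined protocol and SAP*

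**What the plan says.** Under Data Analysis Set, the Per Protocol Set entry has two sentences. The first is "The per protocol set is the subset of the subjects in the full analysis set without treatment crossovers". The second is "In this data set, participants who switch from their randomized treatment will be therefore censored at the time of their switch".

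The Crossovers section defines a crossover as "stop dapagliflozin therapy in the dapagliflozin treatment arm or initiate dapagliflozin in the control arm". It adds that "patients adhering to original randomization arm during the entire follow-up of the study will be analyzed". It labels that analysis post-hoc, yet refers the reader to pre-specified groups. The list of pre-specified subgroups contains no such group.

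The section on managing patients after an event says "If the physician feels appropriate to initiate or to stop SGLT-2 inhibitor therapy, this will always prevail", and then "Crossover will be annotated and patients followed-up according to original plan".

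Under Follow-up Procedures, the telephone form asks about adherence to the assigned arm: "If no, date (month/year) of crossover, and reason for crossover (free text field)".

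Secondary Analysis pre-specifies that the primary and secondary endpoint analyses are repeated in the per-protocol set, to show the effect under ideal circumstances. It does not say which of the two rules applies.

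**The concern.** If the set contains only patients without a crossover, nobody in it is left to censor. If switchers are censored, they belong to the set. An analyst cannot follow both sentences, and the Crossovers section supports the first.

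The choice matters because a switch can be a consequence of the endpoint. Take a control patient who is admitted for HF and then starts dapagliflozin. The first primary event occurred on the assigned arm. Under the drop rule, the patient and the event both leave the analysis. The same happens to a dapagliflozin patient who stops after an event. Membership of the set then depends on the outcome.

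Censoring at the switch avoids this for the primary endpoint only if the event is dated on or before the switch. With a month-and-year switch date, an imputed day can fall before the admission that prompted the switch.

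This is the plan's only estimate offered as the effect under ideal circumstances. In an open-label trial of a prescribable drug, readers will look at it. If the rule is still open at analysis, it can be chosen after the data are seen.

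**Working it through.** **Plan's own figures.** The plan states no per-protocol figure, so the check starts from its sample-size inputs: control 1-year incidence 30%, HR 0.70, two-sided alpha 0.05, power 0.80, 1:1 allocation and 5% withdrawal.

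- Events = 4 × (1.960 + 0.842)² / (ln 0.70)² = 246.8, so 247.
- 247 / 0.255 = 968.6, and 968.6 / 0.95 = 1,020. The stated size is reproduced.
- Expected control events = 510 × 0.30 = 153.
- Treated risk under HR 0.70 = 1 − 0.70^0.70 = 22.1%. The plan's 21% is 0.70 × 30%, a ratio of risks. The hazard-ratio version is used below.

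**Assumptions, not in the documents.**

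- s: HF share of first events.
- q: share of controls with an HF event who then start dapagliflozin.
- r: share of dapagliflozin patients with an HF event who then stop.
- No other switching.

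**Drop rule.** Switchers leave both numerator and denominator:

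- control risk = (0.30 − 0.30·s·q) / (1 − 0.30·s·q)
- dapagliflozin risk = (0.221 − 0.221·s·r) / (1 − 0.221·s·r)
- HR = ln(1 − dapagliflozin risk) / ln(1 − control risk)

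Worked case, s = 0.7, q = 0.3, r = 0. Events removed = 153 × 0.7 × 0.3 = 32. Control risk = 0.237 / 0.937 = 25.3%. HR = ln(0.779) / ln(0.747) = 0.86.

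| s | q | r | HR, formula | HR, simulated |
|---|---|---|---|---|
| 0.5 | 10% | 0 | 0.73 | not run |
| 0.7 | 10% | 0 | 0.74 | 0.74 |
| 0.7 | 20% | 0 | 0.80 | 0.80 |
| 0.7 | 30% | 0 | 0.86 | 0.86 |
| 0.7 | 30% | 10% | 0.80 | 0.80 |
| 0.7 | 30% | 20% | 0.75 | 0.75 |
| 0.7 | 30% | 30% | 0.69 | 0.70 |
| 0.7 | 10% | 30% | 0.60 | 0.61 |

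The simulation used exponential event times, a one-covariate Cox model, a switch within 10 days of the HF event, and 1,000,000 patients per scenario. With no true effect, s = 0.7, q = 0.3 and r = 0 give HR 1.22 under the drop rule and 1.00 under exact censoring. Switching unrelated to outcome, at 5% per year, gave no bias under either rule.

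**Censoring rule.** With exact dates, the triggering event precedes the switch and is kept. The primary-endpoint HR stayed at 0.70 in every event-triggered scenario. With month-and-year dates (s = 0.7, q = 0.3, r = 0), the result depends on the imputed day:

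| Imputed switch day | HR |
|---|---|
| First of month | 0.85 |
| Mid-month | 0.76 |
| End of month | 0.70 |

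**The case against.** The best defence is that one rule was meant. The second sentence is the operative one, and its linking word suggests that crossover-free experience is obtained by censoring. On that reading no event is deleted. The Crossovers text could be a separate exploratory analysis. This is a plausible guess at intent, but the first sentence still says the opposite, and the Crossovers section restates it and points to pre-specified groups.

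Three further objections stand, and they limit what can be claimed.

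- A reader might infer that the plan expects controls to start the drug after an HF event, so that the bias must run against dapagliflozin. The text only permits a switch, in either direction, and the Crossovers section asks physicians to switch only on a clear clinical indication. Stopping in the dapagliflozin arm removes events too, so no sign can be derived.
- A reader might infer that no exact switch date will exist. The month-and-year format is stated for the telephone form only. Patients and physicians are asked to contact the coordinating center before a change, and medical records are reviewed. An exact date may often be obtainable, but the plan does not require one and gives no imputation or tie rule.
- Inverse-probability weighting is not clearly a remedy. With two scheduled contacts and optional follow-up tests, few time-varying predictors of switching will be recorded.

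**Conclusion.** The two definitions conflict, and that follows from the text alone. The drop rule also selects on outcome, because recorded crossovers include switches made after an endpoint event.

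The size rests on assumptions. At a true HR of 0.70 with HF as 50-70% of first events, 10-30% event-triggered starting in controls alone gives about 0.73-0.86. Equal 30% switching in both arms roughly cancels. Ten percent starting in controls with 30% stopping on dapagliflozin gives about 0.61. The censoring rule gives 0.70-0.85 depending on imputation, at 30% control switching and a 70% HF share.

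It would be tempting to conclude that the trial's main result is at risk. It is not: the primary analysis follows randomization regardless of crossovers, and the sample size and alpha are untouched. The point concerns a supportive analysis. It should be corrected before data are seen.

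**What to change.** 1. In the Per Protocol Set entry, delete the restriction to patients with no crossover. Define the analysis as all full-analysis-set patients, censored at first switch, with every event on or before the switch counted.
2. Align the Crossovers section with Secondary Analysis: remove the whole-follow-up adherence wording, the post-hoc label and the pointer to a group that is not listed.
3. Record day, month and year of the switch on the call form and eCRF. State that an event in the admission that led to the switch counts as preceding it, and give an imputation rule for incomplete dates.
4. State whether starting another SGLT-2 inhibitor in the control arm counts as a switch. The Crossovers section names dapagliflozin only, while the study schedule records addition of any SGLT-2 inhibitor.
5. Describe the result as supportive. Note that censoring at a clinically driven switch may be informative, especially for death and CV death, where a patient who switches after an HF event is censored before the outcome. A weighted sensitivity analysis is optional.

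The cost is SAP and protocol wording and one date field. No patients or visits are added.

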Once a potential event is detected either by a local investigator or during a follow-up, a report from the hospital in which the patient is admitted will be requested (with any personal identification of the patient blinded). All events need to be adjudicated by the Clinical Events Adjudication Committee (CEAC). For the evaluation of the events, the local investigator should prepare anonymous copies of the original source of data (clinical reports, complementary tests [catheterizations, ECG, X-ray, etc], lab tests and all relevant information). The regional PI will be responsible for sending the information confidential to the scientific project manager, who will prepare documentation for the CEAC. The CEAC will have a chairman and 3 additional

members. All events will be evaluated by at least 2 members of the CEAC. In the case of controversies, the opinion of the chairman will prevail.

Patients will be followed up for the entire duration of the study regardless of having an adjudicated event. For the composite primary endpoint, the first event will be included in analysis, but for secondary endpoints, different events in the same patients will be individually evaluated.

CENTERS SELECTION

Any center with TAVI program is eligible to participate. During hospital selection, the number of patients discharged with a TAVI during the past 12 months will be evaluated. A minimum number of patients per year (n=12) will be agreed with the hospital. Hospitals not fulfilling the agreed number will eventually be disqualified from recruitment. Hospital with electronic medical records will be prioritized.

RANDOMIZATION AND STRATEGIES FOR RECRUITMENT

Patients will be screened during index hospitalization for TAVI. At discharge (or after discharge provided randomization takes place within 14 days after TAVI), and after informed consent is signed, patients will be randomized to receive or not dapagliflozin. After discharge, patients will be included in each center's TAVI follow-up program (as per local practice).

Randomization will be done via web or via a dedicated mobile application. Each investigator participating in the trial will have a log-in username and password that links her/him to a specific hospital. During randomization, ten fields will be needed to complete:

- 1. Full name of patient
- 2. Telephones (personal and that from relatives)
- 3. Date of TAVI
- 4. DM status.
- 5. Age
- 6. Sex
- 7. Creatinine (mg/dL)
- 8. LVEF (%).

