Primary analyses will be performed in the "full data set" in an intention-to-treat fashion. The intervention arm will be compared against the control arm for the composite primary endpoint. Time-to-event will be evaluated using the Kaplan-Meier survival analysis followed by multivariable Cox proportional hazards model. Hazard ratios (HR) with corresponding 95% confidence intervals will be calculated for treatment effect estimation. All patients without an event will be censored at last day of follow-up. Patients that withdraw from follow-up will be considered censored on the day of withdrawal. Due to the randomization process and the large sample size of the trial, it will be not expected the presence of covariate relevant imbalances between treatment groups. However, for exploratory purpose, standardized differences will be calculated. Those known prognostic factor presenting an imbalance higher than 0.1 standardized difference will be included in the multivariable Cox model. For all tests, we will use 2-sided p-values with alpha ≤0.05 level of significance.

SECONDARY ANALYSIS

The secondary endpoints will be the individual components of the primary composite endpoint, besides CV mortality and the development of new atrial fibrillation. Analyses will be performed following the same guidelines described for primary analysis. Multiplicity adjustment will be not implemented because the hierarchical structure between primary and secondary endponits.

To better explore the treatment effect under ideal circumstances (explanatory approach), primary and secondary endpoint analyses will be replicated in the "per protocol data set" using same methods described above.

SUBGROUP ANALYSIS

All subgroup analyses will be performed using interaction models based on the primary analysis model, also including the subgroup in question and the treatment-subgroup interaction as factors, and presented as treatment hazard ratios for each subgroup and the interaction p-value. Subgroups will be specified in the endpoints section below.

PRE-SPECIFIED SUB-GROUP ANALYSES

- > Diabetic vs non-diabetic patients.
- ightharpoonup LVEF < vs > 40%.
- \geq 80 years vs < 80 years of age on recruitment
- ➤ Males vs females
- ➤ Atrial fibrillation versus sinus rhythm
- > Hypertensive vs normotensive patients
- ➤ Moderate-severe vs mild LVH.
- > Treatment with beta-blockers vs. no beta-blockers

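### The per-protocol set is defined both by excluding crossovers and by censoring at the switch; exclusion deletes pre-switch endpoints and biases the supportive hazard ratio if post-event switching differs by arm

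*Combined protocol and SAP*

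**What the plan says.** **Per Protocol Set (under Data Analysis Set).** Two consecutive sentences define the set. The first is a membership rule: "The per protocol set is the subset of the subjects in the full analysis set without treatment crossovers". The second is a data-handling rule: "In this data set, participants who switch from their randomized treatment will be therefore censored at the time of their switch".

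**Crossovers.** A crossover is stopping dapagliflozin in the dapagliflozin arm or starting it in the control arm. After confirming that the main analysis follows randomization, the section describes a post-hoc analysis in which "patients adhering to original randomization arm during the entire follow-up of the study will be analyzed".

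**Secondary Analysis.** The same kind of analysis is planned in advance: "primary and secondary endpoint analyses will be replicated in the" per-protocol data set, with the methods of the primary analysis.

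**After an event.** Follow-up continues: "Patients suffering a clinical endpoint (including those included in the primary composite) will remain in the study". The section on management after an event also says: "If the physician feels appropriate to initiate or to stop SGLT-2 inhibitor therapy, this will always prevail". Such a change is recorded as a crossover.

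**Which event counts.** Event Adjudication says: "For the composite primary endpoint, the first event will be included in analysis".

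**Date of crossover.** The telephone form under Follow-up Procedures records the crossover date by month and year only.

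**The concern.** If patients with crossovers are outside the set, there is nobody in it to censor. If switchers are censored, they are inside it. Two analysts following this text could build different datasets.

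The datasets differ in their endpoints. Take a control patient with an adjudicated HF admission on day 60 who starts dapagliflozin on day 65. Under censoring, the day-60 event counts. Under exclusion, the patient and the event both disappear because of something that happened afterwards. The plan allows this sequence, since follow-up continues after an endpoint and treatment may be started or stopped then.

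Crossover means starting a drug in one arm and stopping it in the other, in an open-label trial, so the two arms need not switch at the same rate. If they do not, exclusion removes endpoints unevenly. The supportive result could then disagree with the primary result, or appear to strengthen it, for reasons unrelated to the drug. If the choice stays open, it could also be made after results are known.

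**Working it through.** **1. Design figures.** The documents give no crossover rate and no per-protocol HR, so there is no stated figure to reproduce for this set. The design inputs are coherent. The Schoenfeld formula with HR 0.70, two-sided alpha 0.05 and power 0.80 gives 247 events; 247/0.255 = 969; 969/0.95 = 1,020, the planned size; and 1,020 × 0.255 = 260, the stated number of endpoints.

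**2. Inputs for the bias check.**
- From Sample Size: 30% control risk at one year, HR 0.70, one year of follow-up. The dapagliflozin risk at HR 0.70 is 1 − 0.70^0.70 = 22.1%.
- Assumed, not in the documents: 70% of first events are HF events; a share *s* of patients with an HF event then switch, by arm; switching does not alter the hazard.

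**3. Formula.** If *e* is the arm's event risk, exclusion removes 0.70·*e*·*s* from both the numerator and the denominator:

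remaining risk = (*e* − 0.70·*e*·*s*) / (1 − 0.70·*e*·*s*), and HR ≈ ln(1 − dapagliflozin risk) / ln(1 − control risk).

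For 25% of controls and 5% of dapagliflozin patients:
- Control: (0.300 − 0.0525)/(1 − 0.0525) = 0.261.
- Dapagliflozin: (0.2209 − 0.0077)/(1 − 0.0077) = 0.215.
- HR ≈ ln(0.785)/ln(0.739) = 0.80.
- Deleted endpoints per 510: 510 × 0.0525 = 26.8 control and 510 × 0.0077 = 3.9 dapagliflozin.

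**4. Results for exclusion.** The simulation used 400,000 patients per arm, the same assumptions, and 5% per year of unrelated switching in each arm.

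| Switch after HF event (control / dapagliflozin) | True HR 0.70: formula | True HR 0.70: simulation | True HR 1.00: formula | True HR 1.00: simulation |
|---|---|---|---|---|
| 10% / 5% | 0.72 | 0.717 | 1.03 | 1.028 |
| 25% / 5% | 0.80 | 0.798 | 1.14 | 1.131 |
| 50% / 5% | 0.98 | 0.989 | 1.41 | 1.400 |
| 5% / 25% | 0.61 | 0.608 | 0.87 | 0.884 |
| 25% / 25% | 0.69 | 0.691 | 1.00 | 1.005 |

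A second simulation took one third of first events as fatal and varied the unrelated switching. It gave 0.81 for 25%/5%, 0.99 for 50%/0% and 0.60 for 0%/25%. With unrelated switching only (5% to 15%), exclusion gave 0.70 to 0.71.

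**5. Censoring at the switch, composite.** Across both simulations the HR was 0.695 to 0.707 at a true 0.70 and about 1.00 (0.99 to 1.01) at a true 1.00. This follows from the set-up: switching before an event was simulated as unrelated to prognosis.

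**6. Censoring at the switch, death.** A patient who switches after an HF admission is censored when the risk of death is raised. Assumptions: true HR 1.00, HF hazard 0.25 per year, baseline death hazard 0.08 per year, death hazard three to five times higher after HF. With 25%/5% post-HF switching, censoring gave 1.03 to 1.06 and exclusion 1.01 to 1.04. With 50%/5%, censoring gave 1.07 to 1.15 and exclusion 1.02 to 1.10. For death, under these assumptions, censoring is no better than exclusion and slightly worse.

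**The case against.** The strongest reply is that nothing need be dropped. The second sentence says that "participants who switch from their randomized treatment will be therefore censored at the time of their switch". Its connecting word presents censoring as the way the first sentence is carried out, and it is the only one of the two that says how switchers' data are handled. The Crossovers sentence does not name the per-protocol set and may describe a separate analysis of adherers. This reading is available, but the text does not settle it. The membership sentence still excludes switchers, and the Crossovers wording matches exclusion.

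Three other objections stand and limit the point.
- **Switching is permitted, not predicted.** A reader might infer that the protocol expects endpoint-driven crossovers. It gives no rate, and it asks physicians to change treatment only for a clear clinical indication.
- **Every switching rate above is assumed.** A reader might infer that exclusion always biases the HR materially. It does not: 10%/5% moves it only from 0.70 to 0.72, equal switching leaves it essentially unchanged, and 0.99 needs half of the controls with an HF event to start the drug.
- **Censoring is not a complete cure.** A reader might infer that it returns the true HR generally. The composite result depends on prognosis-unrelated switching before an event, and the death results show that it can mislead. The month-and-year crossover date also means the day-60 and day-65 example often could not be ordered from the form alone.

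**Conclusion.** Wrong as written, for a supportive analysis. The two sentences defining the set cannot both hold, the Crossovers section supports the exclusion version, and the analysis is called post-hoc in one place and planned in another. Exclusion deletes adjudicated endpoints that preceded the switch. For the composite, it biases the per-protocol HR when post-event switching differs between arms: towards or beyond 1 if mainly controls switch, and towards exaggerated benefit if mainly dapagliflozin patients do. Around a true 0.70 the assumed scenarios run from about 0.60 to 0.99; equal switching gives 0.69 to 0.70.

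A reader might also infer that the trial's main conclusion is at risk. The documents do not support that. The primary analysis is by randomized arm regardless of crossover, and no stopping rule or alpha depends on the per-protocol set.

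**What to change.** 1. **Per Protocol Set.** Replace the two sentences with one rule: the analysis includes all full-analysis-set patients, follow-up is censored at the first switch, and endpoints on or before the switch count.
2. **Same-month ordering.** State how an event and a switch in the same month are ordered, for example by the medical-record date where available, and otherwise with the event treated as preceding the switch.
3. **Crossovers.** Refer to this rule in place of the restriction to fully adherent patients, and give the analysis the pre-specified status it has under Secondary Analysis.
4. **Caveat.** State that censoring recovers the true HR only if switching before an event is unrelated to prognosis. For all-cause and CV death, add an inverse-probability-of-censoring-weighted sensitivity analysis or label the per-protocol result exploratory.

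The cost is a few sentences of wording, some date checking against medical records, and a little more analysis work. No additional patients are needed, and the primary analysis does not change.
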